9.2 Setting

The observational study will identify two (2) cohorts from each targeted database:

- Efgartigimod Cohort: Patients with an MG diagnosis and who have initiated efgartigimod
- Reference Cohort: Patients with an MG diagnosis and who have not initiated efgartigimod but are on any other therapy for the treatment of MG. Immunoglobulins and plasmapheresis are not considered here, as they are usually used for acute management of MG crisis.

9.2.1 Patient selection (cohort entry)

The overall study population of interest consists of patients with MG and who have initiated efgartigimod and their matched non-exposed cohorts (i.e., reference cohort), who meet study eligibility criteria. Detailed coding algorithms for MG diagnosis ascertainment may vary across databases and will be described in the Statistical Analysis Plan (SAP).

Patient selection for efgartigimod and reference cohorts will occur concurrently and will start when efgartigimod exposure begins to appear in patient records in the database. The earliest cohort entry date (i.e., a patient's index date) for a country depends on the launch date of efgartigimod in that country. To qualify for cohort entry, patients must fulfil the following inclusion criteria.

Inclusion Criteria (efgartigimod cohort)

1. 18 years or older at index date (the date of the first efgartigimod exposure in the database);

2. Patients diagnosed with MG who have initiated efgartigimod³;
3. Patients continuously covered in the data source for at least 3 years before their respective cohort entry date.

Inclusion Criteria (reference cohort)

1. 18 years or older at matched index date.
2. Patients diagnosed with MG who have not initiated efgartigimod treatment, but are on any other therapy for MG.
3. Patients continuously covered in the data source for at least 3 years before their respective cohort entry date.

All patients in the study will have a minimum of 3 years of continuous coverage in the database prior to their cohort entry date. The 3-years minimum prior to index date (lookback period) is required to reliably characterise a patient based on relevant malignancy history, as well as use of other medications prior to initiation of the index medication. The lookback period is also required to reliably identify true initiators of efgartigimod. This lookback period may vary by different data sources: As for the EU databases, a 3-year lookback period is required for US database. However, this period could be adjusted to 1 or 2 years for US database if data for the full period are not available. In that case, sensitivity analyses will be performed for subgroups with 1-2, 2-3 and >3 years lookback period if sample size allows.

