Efgartigimod alfa has marketing authorization for the treatment of patients with gMG in various jurisdictions including the US, Japan, United Kingdom (UK), and the EU. In the US, efgartigimod is approved for the indication of gMG in adult patients who are AChR antibody positive and in the EU and UK it is approved as an add-on to standard therapy for the treatment of adult patients who are AChR antibody positive.

The recommended intravenous (IV) dose of efgartigimod is 10 mg/kg as a 1-hour infusion. The recommended efgartigimod dose administered by a subcutaneous (SC) injection is 1,000 mg efgartigimod alfa to be administered weekly for 4 weeks per cycle. Subsequent treatment cycles

are administered according to clinical evaluation. The frequency of treatment cycles may vary by patient.

Review of literature on cancer immune responses does not suggest that a selective reduction of IgG, without lowering other immunoglobulin isotypes or affecting cell-mediated immunity, would generally increase the risk of developing cancers or have an effect on factors that promote carcinogenesis (Monroy-Iglesias 2022). Evidence from toxicity safety studies has not shown an association between efgartigimod exposure and an increased risk for the development or progression of malignancy.

Study Rationale

In efgartigimod controlled and uncontrolled clinical studies, malignancies have been reported. All reported malignancies were assessed as not being related to efgartigimod. All had confounding factors such as age, medical history, prior or concomitant medications, or limited duration of exposure to efgartigimod. The safety data from studies with efgartigimod in patients with gMG combined with additional data for other immunoglobulin γ (IgG)-reducing agents or treatments did not suggest a correlation between IgG reduction and an increased risk of developing malignancy.

The immune response to cancer is complex and the role of IgG has not been fully elucidated as it can be both procarcinogenic and anti-carcinogenic. However, literature remains controversial and some publications suggest that considering the role of IgGs in tumour-associated immunity and the role of FcRn in antitumour immune surveillance, there is a theoretical risk of developing malignancy in patients treated with efgartigimod. As the mechanism of action of efgartigimod is novel with limited safety data, the role of IgG in the immune response to cancer remains unclear.

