13.1 Analysis populations

All primary and secondary analyses will be conducted in two (2) study cohorts:

1. Efgartigimod cohort: patients with an MG diagnosis and who have initiated efgartigimod for the treatment of MG
2. Reference cohort: patients with an MG diagnosis and who have not initiated efgartigimod, but who are on any other therapy for the treatment of MG

In the exploratory analysis, the long-term risk of malignancies will be evaluated in:

- FcRn cohort: patients with an MG diagnosis and who have initiated other FcRn antagonists for the treatment of MG

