13.2 Primary analysis

The IRR and corresponding 95% CIs will be used to compare the malignancy events among the efgartigimod exposed cohort vs. the reference cohort. The calculations will be performed separately for each individual database and across all three (3) databases as a meta-analysis according to published methods.

A quasi-Poisson regression model will be used to estimate the incidence rate ratio between cohorts with number of event occurrences as the response variable, cohort and age as covariates and follow-up time as offset. Scale/overdispersion parameter will be used to account for potential over- or under-dispersion.

In addition, the balance of baseline measures, including matching variables (i.e. age, sex, CCI and duration of previous MG treatment) and other demographic and disease characteristics, will be assessed. The imbalanced measures which are considered to be potential confounders based on clinical judgement will be added to the quasi-Poisson model as additional covariates.

- Age will be adjusted as a covariate in the quasi-Poisson model to account for the increased malignancy risk over time, no matter balanced or not. And age-specific incidence rates and incidence rate ratio between cohorts can be calculated.
- Concomitant and/or previous use of monoclonal antibody will be adjusted as a covariate in the quasi-Poisson model to account for any potential imbalance.

The primary analyses will be performed on an “as-treated” basis. To this end, patients will contribute person time until the first occurrence of the following events: death, loss to follow-up, end of study period, or a switch from any MG treatment to efgartigimod (for the reference cohort). For the analyses performed based on “as-treated” basis, the time before switching to efgartigimod for the reference cohort will be counted toward the overall person-time but not the time after switching.

A sensitivity analysis based on the intention-to-treat principle will be conducted to ensure the continued monitoring of safety outcomes, irrespective of any treatment modifications throughout the follow-up period. For the sensitivity analyses performed based on “intent-to-treat” basis, both the time before and after switching will be counted. Sensitivity analysis will be described as noted in section 13.5.

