- Users of efgartigimod without concomitant or previous use of another monoclonal antibody vs users of other MG therapies without concomitant or previous use of any monoclonal antibody.

In this analysis patients will contribute person time until the first occurrence of the following events: death, loss to follow-up, end of study period, or a switch from any MG treatment to efgartigimod (for the reference cohort). For the sensitivity analyses performed based on “intent-to-treat” basis, both the time before and after switching will be counted.

Additional considerations regarding the sensitivity analyses will be addressed in the SAP.

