13.5 Exploratory analysis

The long-term risk of malignancies will be explored within a potential new cohort of MG patients who are treated with other FcRn antagonists, if sufficient patients can be identified for this patient cohort.

The study will also assess time to the first occurrence of malignancy overall and specified by type of malignancy using a Fine and Gray model in order to take into account a potential competitive risk for death and cumulative incidence curves will be provided. The index date will be the first claim of efgartigimod (for the efgartigimod cohort) or other MG treatment (for the reference cohort). The proportional hazards assumption will be checked using statistical tests and graphical diagnostics based on the cumulative sums of residuals. If the assumption is violated, an interaction term with time will be added in the model. The study will also assess the healthcare resource utilization (e.g., number of hospitalisations [including MG-related], ER visits, and MG exacerbations and crises) between the efgartigimod and reference cohorts. This exploratory analysis will be descriptive only; details will be provided in the SAP.

In order to assess the robustness of the results, a Proportional Hazard Model (Cox model) will be performed as a sensitivity analysis with providing cumulative incidence curves.

An exploratory analysis of the CPRD dataset (UK) to identify the extent of recorded MG related information will be performed and if feasible, analysis will be adjusted for disease severity.

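### The reference cohort admits and keeps users of other FcRn antagonists, so a class effect on malignancy would pull the primary IRR toward 1 by an amount that depends on an unstated share of person-time

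*Protocol*

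**What the plan says.** **Eligibility.** Reference patients are "Patients diagnosed with MG who have not initiated efgartigimod treatment, but are on any other therapy for MG" (Protocol 9.2.1). Sections 9.1, 9.2 and 13.1 define the cohort in the same way. The one carve-out is in section 9.2: "Immunoglobulins and plasmapheresis are not considered here, as they are usually used for acute management of MG crisis".

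**Censoring.** In the primary as-treated analysis, follow-up ends at death, loss to follow-up, end of study, or "a switch from any MG treatment to efgartigimod (for the reference cohort" (section 13.2). Section 9.2.2 agrees. Starting another FcRn antagonist is not a censoring event.

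**Other FcRn antagonists.** They are recognised as MG treatments, with an exploratory objective (section 8) and an analysis population: "FcRn cohort: patients with an MG diagnosis and who have initiated other FcRn antagonists for the treatment of MG" (section 13.1). That analysis runs only "if sufficient patients can be identified for this patient cohort" (section 13.5).

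**Suspected mechanism.** The Study Rationale in section 7 says that, given the role of IgG in tumour-associated immunity and "the role of FcRn in antitumour immune surveillance, there is a theoretical risk of developing malignancy in patients treated with efgartigimod".

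**Nearest mitigations.** Section 13.2: "Concomitant and/or previous use of monoclonal antibody will be adjusted as a covariate in the quasi-Poisson model". Section 13.4 adds a comparison of antibody-free efgartigimod users with "users of other MG therapies without concomitant or previous use of any monoclonal antibody". Neither names FcRn antagonists.

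**The concern.** Section 9.2.1 describes the matched comparators as not exposed, meaning not exposed to efgartigimod. The hypothesis under test, however, concerns lowering IgG by blocking FcRn, and other FcRn antagonists do that too. Read literally, the protocol lets comparator person-time carry the suspected mechanism while the same drugs are studied elsewhere as an exposure of interest.

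If the risk is a class effect, the reference rate is raised by the drugs' own effect and the IRR shrinks toward 1. In a study set up to look for an important potential risk, that is the unsafe direction: a real increase becomes harder to see. Patients are followed for at least 10 years, so reference patients have ample time to start another FcRn antagonist without being censored.

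**Working it through.** **Inputs from the protocol (section 11, Tables 3 to 5; section 9.1).** Two-sided 5% test of two Poisson rates; rate ratio 1.3; background rate 42.0 per 1,000 PY; 6 years of follow-up; 2:1 matching; 679 efgartigimod patients before and 1,358 after the heterogeneity factor of 2; stated power 86.13%; 1,599 patients anticipated.

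**Assumptions.** A share p of reference person-time is on another FcRn antagonist, and those drugs carry the same true rate ratio of 1.3. The protocol gives no p, so a range is shown.

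**Step 1: reproduce the plan's figure.** Wald test on the log rate ratio with unpooled variance:

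SE² = 1/(n·t·λ₁) + 1/(2n·t·λ₀); power = Φ(ln(IRR)/SE − 1.960).

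Use n = 679, because 1,358 patients count as 679 after the factor of 2. Expected events are 679 × 6 × 0.0546 = 222.4 (efgartigimod) and 1,358 × 6 × 0.042 = 342.2 (reference). SE = √(1/222.4 + 1/342.2) = 0.0861, and ln(1.3) = 0.2624. The ratio is 3.046, so power = Φ(1.086) = 86.13%, as in Table 4. The sample size arithmetic is not at fault.

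**Step 2: dilute the reference.** The reference rate becomes 42.0 × (1 + 0.3p), and the crude IRR becomes 1.3/(1 + 0.3p). At p = 10% the rate is 43.26, reference events are 1,358 × 6 × 0.04326 = 352.5, SE = 0.0856 and IRR = 1.262. The ratio is 2.719, so power = Φ(0.759) = 77.6%.

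| p | crude IRR | power, 42.0 per 1,000 PY, 6 years |
|---|---|---|
| 0% | 1.300 | 86.1% |
| 2% | 1.292 | 84.6% |
| 5% | 1.281 | 82.2% |
| 10% | 1.262 | 77.6% |
| 20% | 1.226 | 66.9% |
| 30% | 1.193 | 54.8% |

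Power passes below 80% at p of about 7.5%.

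**Step 3: the other scenarios.** The same formula at rate ratio 1.3 and p = 10%:

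| background rate per 1,000 PY | 6 years | 8 years |
|---|---|---|
| 42.0 | 77.6% | 88.1% |
| 60.0 | 90.1% | 96.3% |
| 73.6 | 94.9% | 98.6% |

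**Step 4: a larger effect.** With a class rate ratio of 1.5 and p = 30% (42.0 per 1,000 PY, 6 years), the crude IRR is 1.5/1.15 = 1.304 and power is 91.2%. Detection survives, but the estimate is still attenuated.

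These are crude ratios. They take no account of the monoclonal antibody covariate in the primary model.

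**The case against.** **The comparator is the stated one.** The primary objective itself compares efgartigimod with any other MG therapy, and section 9.2.1 implements that consistently. This stands: the document does not contradict itself here, and the contrast should still be reported. It does not answer the point that a product-specific contrast understates a class risk when the comparator holds other members of the class.

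**Existing analyses may help.** If other FcRn antagonists count as monoclonal antibodies, the covariate in section 13.2 absorbs part of the dilution and the antibody-free comparison in section 13.4 removes known users. The protocol does not say that they count. The monoclonal antibodies named in section 7 are eculizumab, ravulizumab and rituximab, and one covariate would pool different mechanisms. The comparisons by background therapy do not name FcRn antagonists either. Section 13.4 also says that sensitivity results are not meant to be inferential.

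**The effect may be small.** The condition on the FcRn cohort suggests that the sponsor is unsure of finding many such patients. At p = 5% power is still 82%. With the anticipated 1,599 patients (effective 799.5) it is 83.9% at p = 10% in the weakest scenario. Section 11 also declares the analysis exploratory. This stands as a limit on size, not on direction.

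**It may be settled in the SAP.** Section 9.2.2.1 defers the handling of patients who switch therapies, but in the context of starting or restarting efgartigimod. Eligibility and primary censoring are already fixed in sections 9.2.1 and 13.2.

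**A stronger reading.** A reader might infer that the same patients will sit in both the reference and the FcRn cohorts. No section says so. Section 13.5 calls the FcRn group a potential new cohort, which could mean a separate one. The documents support only that nothing removes these patients from the reference cohort.

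**Conclusion.** The point holds in conditional form. Followed as written, the protocol counts users of other FcRn antagonists as reference patients and does not censor them when they start such a drug. If malignancy risk is a class effect, the primary IRR is biased toward 1.

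At a class rate ratio of 1.3 and p from 5% to 30%, the crude IRR lies between 1.28 and 1.19, and power in the weakest scenario between 82% and 55%. The figures rest on an equal effect across the class and on a share that the protocol does not state. Without a class effect this bias does not arise.

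It would go too far to say that the study as a whole loses adequate power. At p = 10%, the five other scenarios in Table 4 keep 88% or more.

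**What to change.** - **Section 9.2.1:** exclude from the reference cohort any patient with another FcRn antagonist on or before index. Apply the same prior-use restriction to the efgartigimod cohort, or adjust for prior use, so that the two cohorts are treated alike.
- **Sections 9.2.2 and 13.2:** in the as-treated analysis, end reference person-time at first use of another FcRn antagonist, as is already done for efgartigimod.
- **Sections 13.1 and 13.5:** assign those patients and that time to the exploratory FcRn cohort.
- **Section 13.4:** report the unrestricted comparison with any other therapy, without the new censoring, as a sensitivity analysis.

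**Cost.** The text changes are short. The reference pool becomes somewhat smaller and some person-time is lost. Restricting the efgartigimod cohort, rather than adjusting, would also draw on the margin of 1,599 − 1,358 = 241 patients. The new censoring may be informative if patients who start another FcRn antagonist have more severe MG, which section 15 lists among the confounders that cannot be controlled precisely. The unrestricted analysis helps to gauge this.

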9.1 Study design

This multinational, longitudinal database cohort study will identify patients who are newly treated with efgartigimod and have a diagnostic code for MG (efgartigimod cohort). A patient will be considered an efgartigimod exposed patient if he/she has received at least one (1) dose of efgartigimod.

For each patient entering the efgartigimod cohort, the date of the first efgartigimod exposure in the database (either through an IV infusion or SC injection) will be their index date for the study. Only new users of efgartigimod will be included in this cohort, that is, a patient who receives a first prescription, or first dispensing, or has a first procedure code for efgartigimod during the study period and without a prescription or a dispensing or a procedure code for efgartigimod in the previous 12 months.

A reference cohort will also be selected with a 2:1 ratio to the efgartigimod cohort to provide an overall, real-world assessment of malignancy risk in patients receiving efgartigimod. The reference cohort will consist of patients with a diagnosis code for MG without efgartigimod exposure but is on any other therapy for the treatment of MG during the study period. The index date for each patient in the reference cohort will be assigned as the same index date as the corresponding matched efgartigimod patient.

Identification of patients in the reference cohort will be based on selected matching variables in the patient's history (prior to and including the index date) or within 6 months of the index date. More specifically, within each database, efgartigimod initiators will be matched 2:1 (reference: efgartigimod) by (1) age at index date (+/- 5 years), (2) sex, (3) Charlson Comorbidity Index (CCI)² and (4) duration of prior use of other MG treatment as matching variables prior to and including the index date or within 6 months of the index date.

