9.7 Subpopulations

Subpopulations with increased risk of malignancies will be established by reviewing all patient history in the lookback period, and will be defined as follows:

1. Elderly, age 65 years and older at their index date
2. Chronic use (i.e., ≥ 1 year) of corticosteroids

Lists of relevant codes will be included in the SAP.

10 Data sources

The study will be conducted using

- UK: CPRD
- France: SNDS
- US: Optum Market Clarity

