13.4 Sensitivity analysis

Sensitivity analyses may be considered for scenarios that patients remain on efgartigimod who do not switch vs. patients who take efgartigimod and switch to a different therapy. The sensitivity analysis in this study will be exploratory in nature. Results from subgroup and sensitivity analyses will be presented and discussed in the final report, but it is not the intent to provide any inferential statistics.

- Intention-to-treat analysis will be carried out, in which patients will be censored at death, loss to follow-up, end of study period.
- Sensitivity analyses will be performed for subgroups with 1-2, 2-3 and >3 years lookback period in the US database if sample size allows.
- A sensitivity analysis will be performed for users of efgartigimod as a first-line treatment only if the number of patients allows for it.
- Depending on the number of efgartigimod-using MG patients identified as likely to have been included in the clinical trials, a sensitivity analysis will be carried out by including only patients with a minimum wash-out period of 2 months after the end of the clinical trials.
- To evaluate the potential bias of including events of malignancy occurring within the first year of initiation of efgartigimod or a reference drug, a sensitivity analysis will be conducted that excludes events occurring within the first 12 months after a patient’s study index date.
- To take into account the various reference treatments to which efgartigimod can be added and compared a sensitivity analysis will be performed. In this analysis the reference cohort will be defined according to the type of concomitant treatment given

in addition to efgartigimod (if the number of patients allows). The risk of cancer will thus be assessed between the following treatment groups:

- Users of efgartigimod added to symptomatic treatment (i.e. anticholinesterase agent) vs. Users of symptomatic treatment;
- Users of efgartigimod added to corticosteroids vs. Corticosteroids users;
- Users of efgartigimod added to chronic non-steroidal immunosuppressants vs. Chronic non-steroidal immunosuppressants users;
- Users of efgartigimod added to any chronic immunosuppressants (including corticosteroids) vs. any chronic immunosuppressants users;
- Users of efgartigimod vs other monoclonal antibodies users

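### Optum lookback may vary from 1 to 3 years between patients but is neither matched nor adjusted for, so prevalent cancers can count as incident, unequally if lookback differs by arm

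*Protocol*

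**What the plan says.** Inclusion criterion 3 in protocol section 9.2.1 is the same for both cohorts: "Patients continuously covered in the data source for at least 3 years before their respective cohort entry date". The text below it repeats the rule without exception: "All patients in the study will have a minimum of 3 years of continuous coverage in the database prior to their cohort entry date". It also gives the purpose of the window, which "is required to reliably characterise a patient based on relevant malignancy history, as well as use of other medications prior to initiation".

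The same paragraph then allows the US exception: "However, this period could be adjusted to 1 or 2 years for US database if data for the full period are not available". Section 15 gives the Optum lookback as 1 to 3 years. Section 11 names a shorter look-back among the reasons for assuming that 50% of Optum patients are excluded. Section 13.4 plans for coexisting lengths: "Sensitivity analyses will be performed for subgroups with 1-2, 2-3 and >3 years lookback period in the US database if sample size allows".

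The matching list in section 9.1 is explicit: age, sex, Charlson Comorbidity Index (CCI) and "duration of prior use of other MG treatment as matching variables prior to and including the index date" or within 6 months of it. Section 13.2 names cohort, age and monoclonal antibody use as model covariates, and adds baseline measures found imbalanced and judged clinically to be potential confounders. Lookback length appears in neither place. The primary objective (section 8) restricts to patients without malignancy history in the lookback period, and section 9.6 computes the CCI over the same period.

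**The concern.** A cancer diagnosed two years before index removes a patient with three years of visible history from the primary population. A patient with one year of history stays in if nothing was coded in that year, and a later code for the same cancer can then be counted as a new event. The Optum case definition in section 13.6 (two same-site diagnoses at least 30 days apart) guards against false-positive codes. It does not separate an old cancer under continuing care from a new one.

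The matching variables are affected too. A long-treated patient with one visible year shows at most about one year of prior treatment, and can be paired with someone who has three visible years and is truly newer to treatment. The CCI is likewise measured over unequal windows. Neither the matching nor the named covariates ensures that the arms have similar lookback, so the main Optum comparison has no built-in protection if they do not.

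**Working it through.** **The plan's own figures.** Table 5: 829 × 90% = 746 and 746 × 70% = 522; 681 × 70% = 477; 1,200 × 50% = 600. The total is 1,599, and Optum's share is 600/1,599 = 37.5%.

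Table 3, first row (42.0 per 1,000 PY, 6 years, rate ratio 1.3, 2:1): expected events per patient are 0.042 × 6 = 0.252 in the reference arm and 0.252 × 1.3 = 0.3276 under efgartigimod. The variance of the log rate ratio at n = 679 is (1/0.3276 + 1/0.504)/679 = 0.00742, so SE = 0.0861. Then ln(1.3)/0.0861 − 1.96 = 1.086, and power is 86.13%, as in Table 4. The study-size figures reproduce, and this point does not alter them.

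**Inputs for the bias.** From the protocol: background rate r = 42.0 to 73.6 per 1,000 PY; follow-up t = 6 years; Optum 600 against 1,200. Assumed, because the documents give no figures:
- f, the share of cancers first diagnosed in the dropped years that have no code in the remaining lookback and a code after index: 10% to 50%.
- s, the share of each arm with the short lookback: 70% efgartigimod and 30% reference, or the reverse.

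**Step 1, upper bound.** The share of patients with a cancer first diagnosed in k dropped years is q = 1 − exp(−kr). For k = 1 this is 4.1% to 7.1%; for k = 2 it is 8.1% to 13.7%. These are all such diagnoses, not missed ones. The share that matters is m = f × q.

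**Step 2, null Optum ratio.** IRR = (rt + s_E·m)/(rt + s_R·m), with E for efgartigimod and R for reference.

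Example: r = 0.042, k = 2, f = 50%, so m = 0.50 × 0.0806 = 0.0403. Then (0.252 + 0.7 × 0.0403)/(0.252 + 0.3 × 0.0403) = 0.2802/0.2641 = 1.061.

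**Step 3, pooled ratio.** Add events over the three databases, with a true ratio of 1 in the other two and reference counts halved for the 2:1 ratio. Same example: 1,599 × 0.252 = 402.9; (402.9 + 600 × 0.7 × 0.0403)/(402.9 + 600 × 0.3 × 0.0403) = 419.9/410.2 = 1.024.

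| Rate per 1,000 PY | Years dropped | q | f | Optum IRR, 70/30 | Optum IRR, 30/70 | Pooled IRR, 70/30 |
|---|---|---|---|---|---|---|
| 42.0 | 1 | 4.1% | 10% | 1.006 | 0.994 | 1.002 |
| 42.0 | 1 | 4.1% | 50% | 1.032 | 0.969 | 1.012 |
| 42.0 | 2 | 8.1% | 10% | 1.013 | 0.987 | 1.005 |
| 42.0 | 2 | 8.1% | 50% | 1.061 | 0.942 | 1.024 |
| 73.6 | 1 | 7.1% | 10% | 1.006 | 0.994 | 1.002 |
| 73.6 | 1 | 7.1% | 50% | 1.031 | 0.970 | 1.012 |
| 73.6 | 2 | 13.7% | 10% | 1.012 | 0.988 | 1.005 |
| 73.6 | 2 | 13.7% | 50% | 1.059 | 0.944 | 1.023 |

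**Step 4, equal shares.** With 50% short lookback in each arm, false cases number about 1 to 21 under efgartigimod and 2 to 41 in the reference arm, and the null IRR is exactly 1.00. A true 1.3 is diluted: with m = 0.0403, (0.3276 + 0.5 × 0.0403)/(0.252 + 0.5 × 0.0403) = 0.3478/0.2722 = 1.28.

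**The case against.** The US relaxation covers both cohorts, and nothing in the protocol suggests that efgartigimod patients will have shorter coverage than their references. A reader might infer that false cancers would pile up in one arm and create or hide a signal. The documents do not support that: the false cases arise in both arms, and neither an imbalance nor its direction is shown. An all-or-none split (every efgartigimod patient short, no reference patient short, f up to 50%) would give at most 1.16 in Optum and 1.06 pooled, but nothing points to it.

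A reader might also take 8-14% as the share of misclassified patients. It is only a ceiling. Cancers whose codes recur after index are the likeliest to be coded in the last pre-index year as well, and so to be excluded correctly.

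The protocol has relevant safeguards. Section 13.4 commits to an analysis excluding events in the first 12 months. Section 9.5 foresees chart adjudication if possible. Section 13.2 checks baseline balance and can add covariates. Section 15 acknowledges limited Optum coverage. Section 13 leaves database-specific conventions to the SAP, which is not at hand. These soften the point without closing it. The sensitivity analyses are declared non-inferential, the lookback strata depend on sample size, and the 12-month exclusion neither removes an old cancer recoded later nor repairs the matching variables. The matching list and eligibility rule are fixed in the protocol, so this is not a matter of missing SAP detail.

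Two further criticisms should not be pressed. Splitting matched sets does not by itself invalidate the lookback strata, because section 13.2 states no conditioning on matched sets. Section 9.7 says "Subpopulations with increased risk of malignancies will be established by reviewing all patient history in the lookback period", but a one-year steroid criterion is hard to meet only when lookback is close to 12 months, which does not discredit the whole 1-2 year band.

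**Conclusion.** The point holds as a weakness in a stated design rule. Optum lookback may vary from 1 to 3 years between patients, it determines who counts as malignancy-free and limits what two matching variables can show, and the primary comparison neither matches on it nor names it as a covariate.

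The likely effect is modest. Under the 70/30 and 10-50% assumptions the null Optum ratio is about 1.01-1.06, or 0.94-0.99 with the arms reversed, and the pooled ratio about 1.00-1.02, against a design ratio of 1.3. With equal lookback in the arms there is no bias under the null, only dilution. The recoding share and the arm shares are assumptions; the rates, follow-up and patient numbers are the protocol's. The change is worth making because it is cheap and because the Optum estimate is also reported on its own. The wording of criterion 3 also needs reconciling with the US exception: the exception stands openly in the same section, so this is loose drafting rather than a hidden conflict.

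**What to change.** In section 9.1, add lookback band (1-<2, 2-<3, at least 3 years) as a matching variable for Optum. If that causes too many matching failures, name the band instead as a prespecified covariate in the Optum quasi-Poisson model in section 13.2. The covariate addresses differing false-case rates, but corrects unequal measurement of CCI and treatment duration only in part.

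Keep using all available history to exclude prior malignancy. Cutting it to a common window would admit patients whose earlier cancer is known. State criterion 3 separately for each database so that it agrees with the US exception.

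Cost: some additional matching failures in a database already assumed to lose 50% of its patients, or one more model term. Matching removes the imbalance between bands, so the differential part of the bias goes; the small dilution from prevalent cancers remains and should be acknowledged in section 15.
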